11.9.15.7. Patient Global Impression of Severity

Two PGIS questions will be asked of participants. These questions ask the participant to rate the severity of the impact of their tumor on their ROM and the severity of the impact of their tumor on their physical function, at present.

For both questions, participants are asked to select one of the following responses: "None", "Mild", "Moderate", "Severe", or "Very Severe".

11.9.15.8. End of Part 1 Interview

Participants enrolled in the study will participate in one-on-one telephone End of Part 1 interviews, lasting approximately 60 minutes. These interviews will be conducted by a trained interviewer 1 to 28 days prior to End of Part 1 visit (ie, anytime during Cycle 6), before unblinding. The participant interview will be conducted in the countries where an interviewer is available to conduct in local language.

11.9.16. Clinician Reported Outcome Measures

11.9.16.1. Clinician Global Impression of Change

Three CGIC questions will be asked of clinicians. These questions assess the clinician impression of change in the participant's symptoms, ROM, and physical function, since the start of the study.

The CGIC questions use the same scale as the PGIC.

11.9.16.2. Clinician Global Impression of Severity

Two CGIS questions will be asked of clinicians. The questions ask the clinician to rate their impression of the severity of the impact of the tumor on the participant's ROM and the severity of the tumor-related impact on the participant's physical function, at the time of answering the question.

The CGIS questions use the same scale as the PGIS questions.

11.9.17. Exploratory Assessments

Remaining samples (plasma, whole blood, and tumor tissue) will be stored for up to 15 years after the end of the study. These samples may be used for further analysis intended to address scientific questions related to study drug and/or disease. A decision to perform such exploratory research studies will be based on data obtained from vimseltinib clinical studies, new scientific findings related to the drug class or disease, and/or reagent and assay availability.

11.9.17.1. Tumor Tissue

Tumor tissue sample will be collected as available. Any tumor sample collected prior to Cycle 1 Day 1 and within the last 5 years is acceptable.

Procedures relating to tumor tissue collection are described in a separate laboratory manual.

11.9.17.2. Pharmacokinetic Sample Collection

Pharmacokinetic samples will be collected according to the relevant schedule of assessments. All predose samples should be collected within 60 minutes before dosing. Postdose samples should be collected ± 30 minutes of nominal timepoint. Samples missed or lost for any reason should be recorded. Actual dates and times of blood collection must be recorded.

Pharmacokinetic samples should be collected after the corresponding ECG and vital signs at the same timepoint.

Upon the occurrence of a severe and unexpected AE in an individual participant that the Investigator decides could be related to study drug, a single, ad hoc PK sample may be collected as deemed medically appropriate by the Investigator and Sponsor. The objective in collecting this PK sample would be to investigate any potential association between PK and the unexpected AE. Pharmacokinetic samples will be analyzed by a central laboratory. Details regarding collection, sample handling and shipping are described in a separate laboratory manual.

11.9.17.3. Pharmacodynamic Sample Collection

The objective of collecting these research samples is to investigate the relationship of biomarkers and the medical condition or disease progression. Pharmacodynamic samples will be collected according to the relevant schedule of assessment tables.

Pharmacodynamic samples will be analyzed by multiple laboratories. Details regarding collection, sample handling and shipping will be described in a separate laboratory manual.

Upon the occurrence of a medical condition in an individual participant that the Investigator feels may be related to study drug (eg, a severe and unexpected toxicity) or if a participant experiences disease progression, an ad hoc pharmacodynamic whole blood and plasma sample may be collected as deemed medically appropriate by the Investigator and Sponsor. Collection of such samples would be infrequent and account for no more than 1 additional timepoint in a 28-day cycle for a given participant. Asia and Pacific countries only: whole blood sample will not be collected.

11.9.17.4. Pharmacogenomic Sample Collection

Pharmacogenomic samples will be used to assess germline polymorphisms in genes involved in the metabolism or disposition of vimseltinib. Additionally, the potential relationship between polymorphisms and clinical response and/or study drug-related toxicity will be assessed. A single whole blood sample will be collected prior to dosing for all participants on Cycle 1 Day 1 only.

Details regarding sample collection, processing and shipment will be described in a separate laboratory manual.

11.10. Study Continuation Plan

If a local or national emergency is declared that may impact per-protocol study conduct, then alternative assessments may be implemented after review and approval by the Sponsor to protect participant safety and data quality while minimizing burden.

11.11. Study Termination

When the Sponsor is aware of information on matters concerning the quality, efficacy, and safety of the study drug, as well as other important information that may affect proper conduct of the clinical study, the Sponsor may discontinue the clinical study and send a written notice of the discontinuation along with the reason to the Investigator.

If an Investigator intends to discontinue participation in the study, the Investigator must immediately inform the Sponsor of the discontinuation and the reason for it.

11.11.1. Criteria for Suspension or Premature Termination of the Study

Criteria for either temporary suspension or premature termination of the study include:

1. New information regarding the safety or efficacy of the study drug that indicates a change in the known risk/benefit profile for the compound, such that the risk/benefit is no longer acceptable for participants in the study.

- 2. Significant violation of Good Clinical Practice (GCP) that compromises the ability to achieve the primary study objectives or compromises participant safety.
- 3. The Sponsor may suspend or prematurely terminate the study for reasons not related to the conduct of the study.

11.11.2. Criteria for Premature Termination or Suspension of Investigational Sites

A study site may be terminated prematurely or suspended if the site (including the Investigator) is found to be in significant violation of GCP, protocol, contractual agreement, or is unable to ensure adequate performance of the study.

11.11.3. Procedures for Premature Termination or Suspension of the Study or the Participation of Investigational Site(s)

In the event that the Sponsor elects to terminate or suspend the study or the participation of an investigational site, a study-specific procedure for early termination or suspension will be provided by the Sponsor; the procedure will be followed by applicable investigational sites during the course of termination or study suspension.

12. STATISTICS

12.1. Sample Size Determination

The sample size selection of approximately 120 participants with TGCT (n~80 vimseltinib, n~40 placebo) was based on considerations for powering the analyses of the primary endpoint, key secondary endpoints, detection of rare safety events and overall exposure to vimseltinib, and assuming 15% participant dropout. Participants will be randomized in a 2:1 ratio of vimseltinib versus placebo.

This sample size will have 98% power to detect a statistically significant difference between treatment arms, assuming true ORRs of 35% and 5% in the vimseltinib arm and the placebo arm, respectively, using a two-sided Fisher's exact test at a 5% type I error rate level.

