5. SAMPLE SIZE DETERMINATION

The sample size selection of approximately 120 participants with TGCT (n~80 vimseltinib, n~40 placebo) was based on considerations for powering the analyses of the primary endpoint, key secondary endpoints, detection of rare safety events and overall exposure to vimseltinib, assuming 15% participant dropout. Participants will be randomized in a 2:1 ratio of vimseltinib versus placebo.

This sample size will have 98% power to detect a statistically significant difference between treatment groups, assuming true ORRs of 35% and 5% in the vimseltinib arm and the placebo arm, respectively, using a two-sided Fisher's exact test at a 5% type I error rate level.

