9.10.2. Primary Endpoint

Objective response rate (ORR) per RECIST v1.1 at Week 25 is defined as the proportion of participants with a CR or a PR as the Week 25 Tumor Response (as defined in Table 2) based on IRR per RECIST v1.1. ORR at Week 25 will be compared between the 2 treatment groups using a two-sided Cochran-Mantel-Haenszel (CMH) test stratified by the randomization stratification factors. The test will be performed at a 0.05 alpha level on the ITT Set. A 95% CI for the proportion in each arm using the Clopper-Pearson method as well as the difference in proportion and its associated Wald 95% CI will be presented. A Fisher's exact test and an exact 95% CI for the difference in proportion will be provided as a sensitivity analysis.

No confirmation (ie, CR or PR at the subsequent MRI assessment) will be required for a CR or PR per RECIST v1.1 as this is a randomized study. Complete and partial response will define response for the primary endpoint and additional efficacy analyses.

Determination of an overall response for each timepoint is based on the combination of responses for target lesions, and the presence or absence of one or more new lesions per RECIST v1.1. For this study, determination of the tumor response status for each participant in Part 1 with respect to the primary efficacy endpoint is shown in Table 2 below. All unscheduled assessments prior to Week 25 will be incorporated into the determination of ORR at Week 25 in a similar fashion as Week 13. End of Part 1 scans will be windowed according to Section 8.3. If a participant is missing a scan at Week 25, then they will be considered a non-responder.

Table 2: Definitions of Response for the Primary Efficacy Endpoint

Timepoint Response at Week 13	Timepoint Response at Week 25	End of Part 1 (Week 25) Tumor Response Status
		(Primary Efficacy Endpoint)
CR or PR	CR	Response (CR)
CR or PR	PD	Non-response (PD)
PR	Non-CR/non-PD/non-NE ^a	Response (PR) ^b
SD	CR or PR	Response (CR or PR)
SD	SD	Non-response (SD)
SD	PD	Non-response (PD) ^c
CR, PR, SD, and NE	NE	Non-response (NE)
PD	Any	Non-response (PD)
NE	CR or PR	Response (CR or PR)
NE	SD or PD	Non-response (SD or PD)

Abbreviations: CR=complete response; NE=not evaluated or unevaluable; PD=progressive disease; PR=partial response; SD=stable disease.

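### The stated 98% power includes no loss for the 15% dropout that the sample size is said to assume; if that dropout is scored as non-response, power is about 95%

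*Protocol*

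**What the plan says.** Protocol Section 12.1 and SAP Section 5 each have two paragraphs on sample size.

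- The first explains the choice of about 120 participants (80 vimseltinib, 40 placebo). The reasons are power for the primary and key secondary endpoints, rare safety events and overall exposure. It ends "and assuming 15% participant dropout" in the protocol, with near-identical wording in the SAP.
- The second gives the power. In the protocol: "This sample size will have 98% power to detect a statistically significant difference between treatment arms". The inputs listed there are response rates of 35% on vimseltinib and 5% on placebo, with Fisher's test taken as two-sided at level 0.05. In the SAP: "This sample size will have 98% power to detect a statistically significant difference between treatment groups". Its rates and test are the same.

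The protocol synopsis gives the same 98% and does not mention dropout.

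The primary test is a stratified Cochran-Mantel-Haenszel (CMH) test on the ITT set (Protocol Section 12.4.5.1, SAP Section 9.10.2). On missing scans SAP Section 9.10.2 says: "If a participant is missing a scan at Week 25, then they will be considered a non-responder". The response tables in both documents (Protocol Table 18, SAP Table 2) also make a non-evaluable Week 25 result a non-response.

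**The concern.** A reader who meets a 15% dropout assumption and then a power for this sample size will take that power as allowing for the dropout. Under the plan's own rules, a participant who leaves without a Week 25 scan stays in the denominator as a non-responder. That lowers the observed rate in each arm and narrows the difference between arms. If 35% and 5% describe participants who are scanned, 98% cannot also be the power after 15% dropout.

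This is the only power figure in either document, so it should be clear which conditions it describes. What is at stake is the meaning of that figure. The adequacy of the sample size is not in question.

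**Working it through.** **Inputs.** Group sizes n1 = 80 and n2 = 40; rates p1 = 0.35 and p2 = 0.05; two-sided Fisher's exact test at 0.05; dropout d = 0.15 (all from Protocol Section 12.1 and SAP Section 5). A missing Week 25 scan is a non-response on the ITT set (SAP Section 9.10.2).

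**Formula.** Exact power is the sum, over all x = 0..n1 and y = 0..n2, of Bin(x; n1, p1) × Bin(y; n2, p2), counting only tables (x, y) whose two-sided Fisher p-value is at most 0.05.

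**Step 1: reproduce the plan's figure.** With n = 80 and 40 and rates 0.35 and 0.05, power is 0.9832, or 98.3%. The pooled normal approximation gives 98.4%. The stated 98% is therefore the figure for all 120 participants at the full rates.

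**Step 2: remove the dropouts.** 80 × 0.85 = 68 and 40 × 0.85 = 34. With rates 0.35 and 0.05, power is 0.9634, or 96.3%.

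**Step 3: keep the dropouts as non-responders.** This assumes that 35% and 5% are the rates among those scanned, and that missing a scan is unrelated to response. The rates become p × (1 − d): 0.35 × 0.85 = 0.2975 and 0.05 × 0.85 = 0.0425. With n = 80 and 40, power is 0.9533, or 95.3% (pooled normal 95.1%). The chance of missing the planned effect goes from 1.7% to 4.7%.

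**Step 4: vary the share without a Week 25 scan.** The documents give no arm, timing or cause for the 15%, so the split is an assumption.

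| Missing, vimseltinib / placebo | Rates used | Fisher power |
|---|---|---|
| 0% / 0% | 35% / 5% | 98.3% |
| 5% / 5% | 33.25% / 4.75% | 97.6% |
| 10% / 10% | 31.5% / 4.5% | 96.6% |
| 15% / 15% | 29.75% / 4.25% | 95.3% |
| 20% / 20% | 28% / 4% | 93.7% |
| 10% / 20% | 31.5% / 4% | 97.5% |
| 20% / 10% | 28% / 4.5% | 91.8% |

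**Step 5: the test actually planned.** The unstratified Mantel-Haenszel chi-square, as a stand-in for the stratified CMH test, gives 98.8% with no loss and 96.3% in the Step 3 case. It falls in the same way from a slightly higher start.

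**The case against.** The strongest reply is that nothing has been miscalculated. The power sentence lists its inputs (this sample size, two rates, a test and a level), and 98% follows from them. The 15% is in the paragraph before, among reasons that include the key secondary endpoints. Four of those are repeated-measures change scores, for which dropout does cost information. This stands: there is no arithmetic error in the 98%.

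Second, 35% may already be net of dropout. The endpoint is defined with missing scans as non-response, so its true rate could be the ITT rate, and multiplying by 0.85 would count dropout twice. Protocol Section 5.2 reports 42% at this dose, and 42% × 0.85 = 35.7%. This reading is plausible and cannot be excluded, but neither document makes the link, and both state the dropout separately from the rates.

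Third, dropout is not the same as a missing scan. Protocol Table 1, footnote p, still plans an End of Part 1 MRI for those who stop for reasons other than progression or withdrawal of consent. SAP Sections 8.3 and 8.4.1 allow early-termination visits and unscheduled scans to be mapped to visit windows. Participants who progress are non-responders anyway. This also stands: the 95.3% applies when the full 15% lack a usable scan. The gap does not close completely, because no procedures follow withdrawal of consent (Protocol Section 10.2) and participants lost to follow-up have no scan.

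A reader might go further and infer that the design in fact delivers only 95%, or that 120 is too few. The documents support neither. The 95.3% rests on assumptions that they do not state, and power stays above 91% in every case in the table.

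**Conclusion.** The point holds in a limited, conditional form. The stated 98% is the power with no dropout loss. It becomes about 95% under three assumptions: 15% of each arm lack a Week 25 scan, missingness is unrelated to response, and 35% and 5% are the rates among those scanned. With 10% missing the loss is under 2 points (98.3% to 96.6%). With 5% missing, the result of 97.6% still rounds to the stated figure. If the two rates are already ITT rates with missing scans counted as non-response, 98% is right as it stands.

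The defect is that neither document says which reading applies or how the 15% was used. The consequence is small: at most about 3 points if 15% of each arm are missing, with no effect on the sample size, the test or any decision rule. Severity is minor.

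**What to change.** In Protocol Section 12.1, the synopsis and SAP Section 5, do one of the following:

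- label 98% as the power without dropout, and add that power is about 95% (two-sided Fisher) if 15% of each arm lack a Week 25 scan and are scored as non-responders; or
- if 35% and 5% were meant as ITT rates with missing scans already counted as non-response, say so and keep 98%.

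The cost is one sentence in three places. The first option makes the quoted figure slightly less favourable. The sample size, endpoint and analysis do not change.

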12.2. Randomization and Blinding

The study will randomize approximately 120 participants with TGCT in a 2:1 ratio (vimseltinib:placebo). Randomization will be stratified for tumor location (lower limb/all other) and region (U.S./non-U.S.).

Prior to the unblinding of study data, the Sponsor will approve a comprehensive statistical analysis plan (SAP).

Where required, safety personnel at the Sponsor or designee may be unblinded to a participant's study drug assignment to meet reporting requirements to regulatory agencies. In addition, the Investigator, participant, Sponsor, and study team will be unblinded at the time the participant has disease progression by RECIST v1.1 based on IRR.

Additional Sponsor representatives may be unblinded to some data for the purposes of ensuring adequacy of study conduct, including proper distribution of study drug.

At no point in time before official full study unblinding will any aggregate efficacy and safety analyses by true treatment assignment be conducted by the Sponsor or Sponsor representatives, unless there is explicit permission to do so, for instance high level efficacy assessment for the purposes of a DMC review to determine the adequacy of the risk/benefit profile of the drug as it pertains to the conduct of the clinical study.

12.3. Analysis Set

The Screen Set consists of all participants who have signed the ICF.

The Intent-to-Treat (ITT) Set consists of participants who have been randomized to a study treatment regimen. Analysis will be performed according to the allocated treatment regimen. The ITT population will be the primary analysis set for all the efficacy endpoints analyses.

The Per-protocol (PP) Analysis Set consists of participants in the ITT Set with at least one postbaseline tumor assessment who have no important protocol deviations that are expected to compromise the efficacy and/or safety assessments as follows:

- Violations of key inclusion/exclusion criteria
- Noncompliance with study treatment

- Participant taking wrong study treatment
- Participant receiving prohibited medications or therapies

The efficacy analyses performed on the PP Set will be supportive and treatment group will be based on actual treatment received. Participants with deviations resulting in exclusion from the PP Set will be identified and documented prior to database lock.

The Safety Set consists of participants who have received at least one dose of study treatment. Analysis will be performed according to the treatment regimen actually received.

The PK Set consists of participants in the Safety Set who have at least one evaluable postdose PK sample (or nonmissing postdose PK concentration).

The Pharmacodynamic Set consists of participants in the Safety Set who have at least one pharmacodynamic evaluation.

The PRO Set consists of participants in the ITT Set who have valid baseline and at least one postbaseline PRO assessments.

12.4. Statistical Analyses

12.4.1. General Methods

Data collected in this study will be documented using summary tables and participant data listings. Continuous variables will be summarized using descriptive statistics (number of participants, mean, median, standard deviation, minimum, and maximum). Categorical variables will be summarized using frequencies and proportions. Time-to-event data will be summarized via Kaplan-Meier (KM) methodology using the 25th, 50th (median), and 75th percentiles with associated 2-sided 95% confidence intervals (CIs).

Unless specified otherwise, baseline measurements must be the most recent value prior to receiving the first dose of study drug. If an assessment is not available, then the last assessment prior to that visit would be used.

Medical history, AEs, and concurrent procedures will be coded using Medical Dictionary for Regulatory Activities (MedDRA). Prior and concomitant medications will be coded using the WHO Drug Dictionary.

This study will be broken into 2 periods: the randomized blinded period and the open-label portion that occurs after the study treatment unblinding at Week 25.

Unless specified, the ITT and PP sets are used for efficacy analysis and the Safety Set is used for the safety analysis.

12.4.2. Disposition of Participants

Participant disposition will be summarized overall for all participants who entered the study (ie, signed the informed consent for the study). The number and proportion of participants who entered the double-blind part of the study will be displayed. In addition, the number of participants in each analysis set will be presented. The number and proportion of participants who complete the double-blind part of the study, as well as those who complete the open-label

part of the study will be presented. The number and proportion of participants who discontinue the study will be summarized along with the reason for discontinuation.

12.4.3. Demographic and Baseline Characteristics

Demographic and baseline characteristics at study entry will be summarized for the ITT, safety, and PP analysis sets. Medical history will be summarized overall for the Safety Set.

12.4.4. Extent of Exposure

The total number of participants who received study medication will be summarized by frequency and percentage. In addition, the number of cycles received will be displayed using both categorical and continuous descriptive statistics. These summaries will be performed for the Safety Set.

12.4.5. Efficacy Analyses

12.4.5.1. Primary Efficacy Analysis

Objective response rate is defined as the proportion of participants with a CR or a PR based on IRR per RECIST v1.1. Objective response rate at Week 25 will be compared between the 2 treatment arms using a two-sided Cochran-Mantel-Haenszel test stratified by the randomization stratification factors. The test will be performed at a 0.05 alpha level on the ITT set. A 95% CI for the proportion in each arm and for the difference in proportion will be presented.

No confirmation (ie, CR or PR at the subsequent MRI assessment) will be required for a CR or PR per RECIST v1.1 for a randomized study. Complete and partial response will define response for the primary endpoint and additional efficacy analyses.

Determination of an overall response for each timepoint is based on the combination of responses for target lesions, and the presence or absence of one or more new lesions. For this protocol, determination of the tumor response status for each participant in Part 1 with respect to the primary efficacy endpoint is shown in Table 18.

Response at Week 13	Response at Week 25	End of Part 1 Tumor Response Status (Primary Efficacy Endpoint)
CR or PR	CR	Response (CR)
CR or PR	PD	Non-response (PD)
PR	Non-CR/non-PD/non-NE ^a	Response (PR) ^b
SD	CR or PR	Response (CR or PR)
SD	SD	Non-response (SD)
SD	PD	Non-response (PD) ^c
CR, PR, SD, and NE	NE	Non-response (NE)

 Table 18:
 Definitions of Response for the Primary Efficacy Endpoint

Response at Week 13	Response at Week 25	End of Part 1 Tumor Response Status (Primary Efficacy Endpoint)
PD	Any	Non-response (PD)
NE	CR or PR	Response (CR or PR)
NE	SD or PD	Non-response (SD or PD)

Abbreviations: CR=complete response; NE=not evaluated or inevaluable; PD=progressive disease; PR=partial response; SD=stable disease.

^a Neither sufficient shrinkage to qualify for CR nor sufficient increase to qualify for PD, taking as reference the nadir at Week 13.

^b A tumor that has achieved the criteria of PR will be considered an ongoing PR until progressive disease is objectively documented.

^c To be considered SD, the tumor must achieve the criteria for SD at the Week 25 visit; shorter duration SD will not be considered SD at the End of Part 1.

